3.2. RANDOMIZATION STUDY

This Phase I/II, randomized, blinded, placebo-controlled study is designed to evaluate the safety and tolerability of allo-hMSCs in subjects with Frailty and to explore potential efficacy at 3 and 6 months.

Approximately fifteen (15) subjects will be enrolled in the pilot phase and thirty (30) subjects with Frailty will be enrolled in the randomized phase for a total of up to forty-five (45) subjects. In the randomized phase, subjects will then be enrolled and randomized

1:1:1 to an active arm or placebo. Additional subjects may be enrolled if deemed appropriate.

Eligible subjects must have a diagnosis or symptoms of frailty as defined by the Canadian Study on Health & Aging². Following informed consent before or at the screening visit, the diagnosis of frailty will be confirmed by investigator review of medical history.

In the randomized phase of the trial, electronic randomization will be performed using the Advantage EDC system and communicated to cellular laboratory personnel who have no contact with the investigators or subjects. At the time of administration, opaque tubing will be used to maintain double blinding. Treatments will be administered once and will consist of 1×10^8 allo-hMSCs (100 million cells), 2×10^8 allo-hMSCs (200 million cells), or placebo. After each infusion, subjects will be monitored for immediate complications.

Continued safety and tolerability with review of adverse events (AEs) will be monitored at each visit. Efficacy parameters (Gait speed, handgrip strength, and QOL questionnaires) will be assessed following Day 0 until Month 6. Clinical laboratory tests to assess safety will be performed at every clinic visit, excluding the baseline visit and month 12 visit.

In the randomized phase of the trial, subjects who received placebo will have the option to receive 1×10^8 (100 million) cells of allogeneic hMSCs, if all study endpoints are met. If all endpoints are met then the subject will be administered the study drug and follow the study schedule listed in Section D.14 (Table D1) of Addendum D after subjects in the randomized phase have been unblinded.

4. SUBJECT SELECTION

4.1 Inclusion Criteria

In order to participate in this study, a subject MUST:

1. Provide written informed consent.
2. Subjects age ≥ 60 and ≤ 95 years at the time of signing the Informed Consent Form.
3. Show signs of frailty apart from a concomitant condition as assessed by the Investigator with a frailty score of 4 to 7 using the Canadian Clinical Frailty Scale
4. Female subjects must have an FSH ≥ 25.8 mIU/mL, if not currently on hormone replacement therapy.

4.2 Exclusion Criteria

In order to participate in this study, a subject MUST NOT:

1. Score of ≤ 24 on the Mini Mental State Examination (MMSE)

2. Inability to perform any of the assessments required for endpoint analysis (report safety or tolerability concerns, perform PFTs, undergo blood draws, read and respond to questionnaires).
3. Active listing (or expected future listing) for transplant of any organ.
4. Clinically important abnormal screening laboratory values, including but not limited to: hemoglobin <8 g/dl, white blood cell count <3000/mm³, platelets<80,000/mm³, INR > 1.5 not due to a reversible cause (i.e. Coumadin), aspartate transaminase, alanine transaminase, or alkaline phosphatase > 3 times upper limit of normal, total bilirubin > 1.5 mg/dl.5.
5. Serious comorbid illness that, in the opinion of the investigator, may compromise the safety or compliance of the subject or preclude successful completion of the study. Including, but not limited to: HIV, advanced liver or renal failure, class III/IV congestive heart failure, myocardial infarction, unstable angina, or cardiac revascularization within the last six months, or severe obstructive ventilatory defect.
6. Any other condition that, in the opinion of the investigator, may compromise the safety or compliance of the subject or preclude successful completion of the study.
7. Be an organ transplant recipient.
8. Have a clinical history of malignancy within 3 years (i.e., subjects with prior malignancy must be disease free for 3 years), except curatively-treated basal cell carcinoma, squamous cell carcinoma, melanoma in situ or cervical carcinoma if recurrence occurs.
9. Have a non-pulmonary condition that limits lifespan to < 1 year.
10. Have a history of drug or alcohol abuse within the past 24 months.
11. Be serum positive for HIV, hepatitis BsAg or Viremic hepatitis C.
12. Be currently participating (or participated within the previous 30 days) in an investigational therapeutic or device trial.
13. Be a female who is pregnant, nursing, or of childbearing potential while not practicing effective contraceptive methods. Female subjects must undergo a blood or urine pregnancy test at screening and within 36 hours prior to infusion.
14. Hypersensitivity to dimethyl sulfoxide (DMSO).

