addendum for its exclusion criteria)	
a blood or urine pregnancy test at screening and within 36 hours prior to infusion.
 
 3. Inability to perform any of the assessments required for endpoint analysis. 4. Active listing (or expected future listing) for transplant of any organ. 5. Clinically important abnormal screening laboratory values. 6. Serious comorbid illness that, in the opinion of the investigator, may compromise the safety or compliance of the subject or preclude successful completion of the study. 7. Hypersensitivity to dimethyl sulfoxide (DMSO). 8. Be an organ transplant recipient. 9. Have a clinical history of malignancy within 3 years (i.e., subjects with prior malignancy must be disease free for 3 years), except curatively-treated basal cell carcinoma, squamous cell carcinoma, melanoma in situ or cervical carcinoma, if recurrence occurs. 10. Have a non-pulmonary condition that limits lifespan to < 1 year. 11. Have a history of drug or alcohol abuse within the past 24 months. 12. Be serum positive for HIV, hepatitis BsAg or Viremic hepatitis C. 13. Be currently participating (or participated within the previous 30 days) in an investigational therapeutic or device trial. 14. Any other condition that, in the opinion of the investigator, may compromise the safety or compliance of the subject or preclude successful completion of the study.
--------------------------------------	--

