Subjects in the pilot phase that received one (1) infusion of allogeneic MSCs are eligible to participate in this optional follow-on phase for a second dose. Because several studies, reviewed below, have now shown safety of repeat doses of MSCs in a variety of medical conditions, additional safety testing in the subject population of aging frailty enrolled in the CRATUS trial is required⁹². All study specific processes and procedures included in the pilot phase of the protocol apply in this addendum unless otherwise noted.

A.2 Demonstrated Safety and Increased Efficacy of Multiple Infusions of Allogeneic Mesenchymal Stem Cells

Active clinical trials and ongoing preclinical work provide an accumulating data set supporting the safety and, in some cases, therapeutic efficacy of allogeneic mesenchymal stem cells (MSCs). Allogeneic mesenchymal stem cells are both immunoprivileged and immunosuppressive, thereby enabling their use as an allograft⁹³. Cellular therapy with allogeneic MSCs has abundant support from both animal studies and human clinical trials for a wide range of disorders (Table 1). For example, the POSEIDON study addressed the major issue of the use of allogeneic MSCs as a cell-based therapeutic¹⁸. In this study, subjects with cardiac failure were randomized to receive either autologous MSCs or identically prepared allogeneic MSCs from healthy donors.

Accumulating evidence also supports the concept that repeated doses and/or co-administration of allogeneic MSCs could further enhance therapeutic outcomes. This is an extremely important area for medical investigation, since repeat dosing could potentially have an additive effect and/or reverse disease pathology, depending on the disorder.

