5. Serious comorbid illness that, in the opinion of the investigator, may compromise the safety or compliance of the subject or preclude successful completion of the study. Including, but not limited to: HIV, advanced liver or renal failure, class III/IV congestive heart failure, myocardial infarction, unstable angina, or cardiac revascularization within the last six months, or severe obstructive ventilatory defect.
6. Any other condition that, in the opinion of the investigator, may compromise the safety or compliance of the subject or preclude successful completion of the study.
7. Be an organ transplant recipient.
8. Have a clinical history of malignancy within 3 years (i.e., subjects with prior malignancy must be disease free for 3 years), except curatively-treated basal cell carcinoma, squamous cell carcinoma, melanoma in situ or cervical carcinoma if recurrence occurs.
9. Have a non-pulmonary condition that limits lifespan to < 1 year.
10. Have a history of drug or alcohol abuse within the past 24 months.
11. Be serum positive for HIV, hepatitis BsAg or Viremic hepatitis C.
12. Be currently participating (or participated within the previous 30 days) in an investigational therapeutic or device trial. This does not exclude subjects that participated in the pilot phase.
13. Be a female who is pregnant, nursing, or of childbearing potential while not practicing effective contraceptive methods. Female subjects must undergo a blood or urine pregnancy test at screening and within 36 hours prior to infusion.
14. Have hypersensitivity to dimethyl sulfoxide (DMSO)

A.5 Dosing

After subjects complete their Month 12 follow-up phone call visit in the pilot phase (first infusion), all 15 subjects will then have the option of receiving additional infusions of allogeneic hMSCs: 1×10^8 (100 million) cells delivered via peripheral intravenous infusion.

The Allo-hMSCs will be derived from donors meeting criteria for allogeneic unrelated human bone marrow stem cell source manufactured by the University of Miami.

A.6 Dosage Rationale

A safety profile for IV infusion of hMSCs was based on results from previous completed toxicology results (Hare et al. 2277-86). The results from previous studies demonstrate that the product can be administered intravenously without toxic events at up to 65 x 10^6 hMSC/kg dose delivered in one bolus infusion or at 100 x 10^6 hMSC/kg cumulative dose delivered by 5 infusions (20 x 10^6 hMSC/kg per infusion).

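### All six exclusion lists exempt four curatively treated cancers only if recurrence occurs, which contradicts the curative-treatment and disease-free terms of the same sentence

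*Combined protocol and SAP*

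**What the plan says.** Item 8 of section 4.2 sits under the lead-in "In order to participate in this study, a subject MUST NOT". Its base rule is "Have a clinical history of malignancy within 3 years (i.e., subjects with prior malignancy must be disease free for 3 years". An exemption for four cancers follows, and it closes with the condition at issue: "except curatively-treated basal cell carcinoma, squamous cell carcinoma, melanoma in situ or cervical carcinoma if recurrence occurs".

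The synopsis has the same rule as item 9, with a comma before the condition: "melanoma in situ or cervical carcinoma, if recurrence occurs". Addenda A, B, C and D repeat it as item 8 of their exclusion lists (A.4.2, B.3.2, C.4.2, D.4.2), without the comma: "melanoma in situ or cervical carcinoma if recurrence occurs". No section explains the phrase or states a different condition.

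Three neighbouring items in 4.2, repeated in the addenda, can reach some of the same subjects. Item 5 covers serious comorbid illness in the investigator's opinion. Item 6 covers "Any other condition that, in the opinion of the investigator, may compromise the safety or compliance of the subject". Item 9 covers non-pulmonary conditions that limit life to under a year.

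**The concern.** In a list of things a subject must not have, an exception lets people in. Here the exception opens only when the cancer comes back. That is the opposite of what one expects from a sentence that also requires curative treatment and 3 disease-free years.

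The rule is applied more than once. Section 6.2 offers pilot subjects further infusions only while they still meet the criteria. Each addendum carries its own copy of the list, and Addendum C spaces infusions 6 to 18 months apart. A recurrence between infusions would put this clause to use.

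The primary objective is safety. Death and laboratory abnormalities judged clinically significant are components of the one-month TE-SAE composite (2.2.1). Death from any cause is a secondary endpoint (2.2.2), and 1-year survival is named among the exploratory aims (2.1.1). Events due to a recurrent cancer could enter those results. The rationale in A.2 also states "Allogeneic mesenchymal stem cells are both immunoprivileged and immunosuppressive", although the documents draw no link between that property and cancer recurrence.

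**Working it through.** No arithmetic applies. The check is to write the criterion as a logical statement and compare outcomes.

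**Terms, all from item 8.** M: malignancy within 3 years, or not disease free for 3 years. L: one of the four listed cancers. C: curatively treated. R: recurrence occurs.

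**Reading 1, literal.** Excluded = M and not (L and C and R).

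**Reading 2, literal, but a recurrence is taken to show that treatment was not curative.** C and R can then never both hold, so the exemption is empty and excluded = M.

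**Reading 3, elliptical.** The listed cancers are exempt, and the exemption is lost on recurrence. Excluded = M and not (L and C and not R).

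| Subject | Reading 1 | Reading 2 | Reading 3 |
|---|---|---|---|
| Listed cancer, cured, disease free under 3 years, no recurrence | excluded | excluded | not excluded |
| Listed cancer, curative treatment given, recurred within 3 years | not excluded | excluded | excluded |
| Listed cancer, disease free 3 years or more | not excluded | not excluded | not excluded |
| Any other malignancy within 3 years | excluded | excluded | excluded |

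The table shows three things.

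1. The last two rows do not depend on the reading. The defect is confined to listed cancers inside the 3-year window.
2. Both literal readings exclude the cured subject without recurrence, whom an exemption for curatively treated cancer would be expected to keep.
3. For the recurrent subject, the outcome turns on whether treatment followed by recurrence still counts as curative. The text does not say.

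**Do other items settle it?** For the recurrent subject, items 5 and 6 allow exclusion but depend on opinion, and item 9 applies only if life expectancy is under a year. For the cured subject, no item can reverse an exclusion under item 8. Enrolling that person would be a deviation on the literal text. Section 4.4 has no withdrawal criterion specific to recurrence, only medical reasons at the investigator's discretion.

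**Is it an extraction fault?** The same phrase in six separately placed lists makes that unlikely.

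**The case against.** The strongest reply is that any competent site will understand the clause as Reading 3. The synopsis comma helps that reading, and it fits the rest of the sentence. It probably is what was meant. But the words state recurrence as the condition for the exemption, and getting to Reading 3 means supplying words that are not there. Two screeners could classify the same subject in opposite ways, each relying on the protocol.

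A second reply is that a subject with active recurrence can hardly be called curatively treated, so item 8 does not let that subject through. This has force: it is Reading 2. It weakens the recurrent-cancer half of the concern and leaves the cured-subject half intact.

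A third is grammatical. In the five lists without the comma, the condition could attach to cervical carcinoma alone. The defect would then be narrower, but the contradiction would remain for that cancer.

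A reader might infer more than the documents support:

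- **That sites will enrol subjects with recurrent cancer.** Not being excluded by item 8 is not enrolment, because items 5, 6 and 9 still apply.
- **That cured subjects are shut out in general.** Those disease free for 3 years or more stay eligible.
- **That any hospital admission for recurrent cancer would count in the primary composite.** Only admission for worsening dyspnea is a component.
- **That randomized subjects would carry this exposure through repeated dosing.** They receive one infusion, and placebo subjects may have one optional cell infusion under Addendum D. The four-infusion maximum belongs to pilot and Addendum B subjects.

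**Conclusion.** The point holds as a drafting and internal-consistency defect in an operative eligibility rule. In all six lists the condition on the exemption conflicts with the curative-treatment and disease-free terms of its own sentence, and nothing else in the protocol resolves the conflict.

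Its size cannot be put as a count. The documents give no prevalence of the listed cancers, no number screened, and no account of how the clause has been applied. For scale only, if one subject were wrongly admitted, that would be 1/10 = 10% of a randomized arm or 1/5 = 20% of a pilot dose group. Neither figure estimates how often this would happen. No sample size, boundary or planned analysis changes.

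The conclusion that cured subjects are excluded rests only on taking the condition as written. The conclusion that item 8 fails to exclude a recurrent case also needs treatment followed by recurrence to count as curative.

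**What to change.** Reconcile the condition with the rest of the sentence in all six places: synopsis item 9, and item 8 of 4.2, A.4.2, B.3.2, C.4.2 and D.4.2. The wording consistent with the sentence's own terms is *provided no recurrence has occurred*. The sponsor should confirm that this is the intent and make clear that it governs all four cancers. The punctuation should match across the lists.

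The cost is one phrase in six lists, carried in an amendment with the ethics approval that section 10.2 already requires. There is no effect on sample size or analysis. Addendum C (C.1) reports that 12 subjects have had two doses and that 20 have had one dose of antibiotic-free cells. The correction therefore mainly serves the screening and re-screening still to come. For subjects already screened, a short check of whether anyone had a listed cancer within 3 years, and how item 8 was applied, would show whether the wording affected any decision.

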1.2 Mesenchymal Stem Cells

Mesenchymal stem cells (MSCs) are multipotent cells capable of differentiating into a number of different cell lines. Because of their unique combination of multipotency, migratory ability, and immunoprivileged state (MSCs do not express major histocompatibility factor-II making allogeneic transplant possible)³¹, interest has abounded regarding their potential therapeutic and regenerative applications. In fact, MSCs have been shown to hold promise as a novel therapeutic agent in multiple disease processes. Treatment with MSCs has been shown to ameliorate severe graft versus host disease³¹, contribute to pancreatic islet and renal glomerular repair in diabetes³², attenuate sepsis³³, reverse fulminant hepatic failure³⁴, protect against ischemic acute renal failure³⁵, reverse remodeling³⁶⁻³⁸ and improve cardiac function after myocardial infarction¹⁷, to be a potential source of multiple cell types for use in tissue engineering^{39;40}, and to be capable of tissue regeneration after spinal cord trauma, stroke, and connective tissue injury⁴¹⁻⁴³.

In the lung, MSCs have been shown to contribute to tissue regeneration after elastase-induced emphysema⁴⁴, home to sites of asbestos induced lung injury⁴⁵, contribute to tissue remodeling in a rat monocrotaline model of pulmonary hypertension⁴⁶, decrease chronic airway inflammation in a murine ovalbumin model of asthma⁴⁷, and to restore alveolar fluid balance after endotoxin induced acute lung injury⁴⁸.

Tracking of radioactively labeled cells shows that when administered intravenously, MSCs localize primarily to the lung, followed by the liver, and then other organs⁴⁹. A number of studies show that MSCs preferentially home to sites of injury in the lung and contribute to tissue regeneration and repair⁵⁰⁻⁵⁶. Using Y-chromosome fluorescence in-situ hybridization, Y-chromosome positive male MSCs can be found at sites of lung injury in transplanted female mice^{51;52;55}. These male MSCs appear to adopt anepithelial cell morphology, suggesting that they contribute to tissue regeneration either by fusion with resident epithelial cells or by mesenchymal to epithelial transition⁵¹.

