2. STUDY OBJECTIVES AND ENDPOINTS

2.1 Study Objectives

2.1.1 Primary Objective

- To demonstrate the safety of intravenous allogeneic hMSCs administered in subjects with Frailty and to explore treatment efficacy (decrease in frailty, frequency of acute exacerbations, change in symptom related quality of life, improved cardiovascular status, decrease in inflammatory biomarkers, endothelial function and 1 year survival).

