2.2 Study Endpoints

2.2.1 Primary Endpoints (Safety)

- Safety (Primary): Incidence (at one month post infusion) of any treatment-emergent serious adverse events (TE-SAEs), defined as the composite of: death, non-fatal pulmonary embolism, stroke, hospitalization for worsening dyspnea and clinically significant laboratory test abnormalities, determined per the Investigator's judgment.
- Serum chemistry: chloride, sodium, Carbon Dioxide, BUN, creatinine, glucose, calcium, AST/SGOT, ALT/SGPT, total bilirubin (fractionate if total > 1.5 times normal), alkaline phosphatase, albumin,
- Hematology (CBC): hemoglobin, hematocrit, platelets, WBC, WBC differential

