2.2.2 Secondary Endpoints (Efficacy)

The following efficacy endpoints will be evaluated in this trial (During the screening, baseline, Month 3 and/or Month 6 visits):

1. Difference in rate of decline of Frailty defined as:
 - a. Reduced Activity (assessed via CHAMPS questionnaire)

- b. Slowing of Mobility (assessed via a 4 meter gait speed test and SPPB assessment)
- c. Weight Loss
- d. Diminished handgrip strength (assessed via dynamometer)
- e. Exhaustion (assessed via the MFI questionnaire)
- f. Decrease in subject quality of life assessment(s) (assessed via ICECAP, SF-36, EQ-5D Questionnaires)

2. Death from any cause.
3. Change between screening and 6 months in dobutamine stress echo induced ejection fraction.
4. Change between screening and 6 months for the following panel of inflammatory markers: CRP, IL-6, D-dimer, fibrinogen, CBC with differential, and TNFa

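### The under-1-year life-expectancy exclusion exempts pulmonary conditions although the indication is frailty, leaving some terminal lung disease to investigator discretion alone

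*Combined protocol and SAP*

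**What the plan says.** The life-expectancy criterion is item 9 of Section 4.2: a subject must not "Have a non-pulmonary condition that limits lifespan to < 1 year". The same wording is item 10 of the synopsis exclusions and item 9 of A.4.2, B.3.2, C.4.2 and D.4.2.

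The indication is set by inclusion item 3 in Section 4.1, under which a subject must "Show signs of frailty apart from a concomitant condition as assessed by the Investigator with a frailty score of 4 to 7" on the Canadian Clinical Frailty Scale. No inclusion criterion asks for lung disease.

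Two other exclusions in Section 4.2 could reach lung disease through judgment. Item 5 opens with "Serious comorbid illness that, in the opinion of the investigator, may compromise the safety or compliance of the subject or preclude successful completion of the" (the sentence ends with the trial itself); its examples are open-ended, and the one lung example is severe obstructive impairment. Item 6 is a catch-all on the same test.

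On where the cells go, Section 1.2 states that "when administered intravenously, MSCs localize primarily to the lung, followed by the liver, and then other organs". The primary safety endpoint in Section 2.2.1 is the one-month incidence of a composite of "death, non-fatal pulmonary embolism, stroke, hospitalization for worsening dyspnea and clinically significant laboratory test abnormalities, determined per the Investigator's judgment". Section 2.1.1 ends its list of exploratory aims with "decrease in inflammatory biomarkers, endothelial function and 1 year survival", and Section 2.2.2 lists "Death from any cause" among the secondary endpoints.

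**The concern.** A life-expectancy exclusion normally keeps out subjects whose own disease is likely to produce deaths and admissions during follow-up. Exempting lung conditions makes sense when a lung disease is under study, because otherwise the criterion would remove the target population. In a frailty trial it has no evident purpose. It also treats equal prognoses unequally: under a year to live from heart, liver or neurological disease is a firm bar, but the same outlook from lung disease is not.

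The exempted organ is not incidental to this trial. By the protocol's own account it is where intravenous cells first localize, and two components of the primary composite are pulmonary or respiratory. At stake are consistent eligibility decisions, the safety margin for a small group of candidates, and the readability of event counts in very small groups.

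**Working it through.** The plan has no figure to reproduce here. Section 9.1 says the sample size had no formal justification, and the point is mainly textual.

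**1. Is the wording isolated?** No. It is the same in all six eligibility lists, so it is the operative rule for every phase. In Addenda A and C it is applied again when a subject returns for another infusion, so it also governs lung disease that has developed since entry.

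**2. Does the indication explain it?** No. Sections 4.1 and 3.2 define the population by frailty.

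**3. Where might it come from?** Table 1 in Section 1.5 is titled as a summary of animal studies for IPF. Section 4.4 asks for lung function data on withdrawn subjects, and Section 9.2 plans a descriptive summary of lung function. These suggest text carried over from a lung-disease protocol. That is an inference, and the second and third signs are weak because Table 2 does schedule FEV-1 in this trial.

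**4. What do the other criteria in Section 4.2 catch?**

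| Item | Firm or discretionary | Lung subjects removed | Lung subjects left |
|---|---|---|---|
| 2, inability to do assessments, naming PFTs | Firm | Those who cannot perform the tests | Those who can perform them, whatever the result |
| 3, transplant listing | Firm | Listed or expected to be listed | Not candidates |
| 8, malignancy within 3 years | Firm | Recent lung cancer | Non-malignant disease |
| 5, serious comorbid illness | Investigator opinion | Severe obstructive disease is named; others if so judged | Non-obstructive disease not so judged |
| 6, any other condition | Investigator opinion | Any, if so judged | Any not so judged |

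Inclusion item 3, which asks for frailty apart from a concomitant condition, adds a further check, also made by the investigator.

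**5. What is left?** Terminal lung disease that is non-malignant and non-obstructive (for example fibrotic or pulmonary vascular), in a subject who is not a transplant candidate and can perform the tests. No firm criterion applies to that subject. The synopsis gives less guidance: its comorbidity item has no examples and its assessments item does not mention PFTs, so its only lung wording among the exclusions is the exemption itself.

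**6. What does one background event do?** Section 6.2 gives 5 subjects per pilot group and 10 per randomized arm. With x events in n subjects, the rate is x/n. The exact (Clopper-Pearson) 95% limits are the 0.025 quantile of Beta(x, n−x+1), taken as 0 when x = 0, and the 0.975 quantile of Beta(x+1, n−x).

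- Pilot group: 0/5 = 0% (0 to 52.2%); 1/5 = 20% (0.5 to 71.6%).
- Randomized arm: 0/10 = 0% (0 to 30.8%); 1/10 = 10% (0.3 to 44.5%).

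The composite in Section 2.2.1 does not ask whether an event is related to the cells. The closing reference to investigator judgment, which in the synopsis attaches to the laboratory component, is not a causality test. A death or dyspnea admission within one month from pre-existing lung disease therefore counts in full. Sections 9.3 and 9.4.3.3 have the DSMB use 30-day pilot data to keep or modify the randomized doses, so the pilot count has a practical use.

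**The case against.** The strongest reply is that the safeguards overlap and little gets through. Items 2, 3 and 8 are firm and remove many subjects with advanced lung disease. Item 5 is not confined to its examples, and its test, whether the subject can complete the study, bears directly on someone with under a year to live in a trial with 12-month contact. This largely stands: the residual group is narrow, and a reader who infers that a subject dying of lung disease is therefore eligible goes further than the documents allow. What does not stand is that discretion equals a firm rule. The plan chose a firm rule for every other organ, and an explicit exemption may suggest to an investigator that lung conditions were meant to be admitted.

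A reader might also infer that background lung events would be taken for cell toxicity. The documents do not support that. Section 8.11 has the investigator weigh the natural history of underlying disease when judging causality, Section 9.4.2 gives the DSMB unblinded safety data by group, and the randomized phase has a placebo arm. The events would still enter the composite count, but attribution to the cells does not follow.

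Nor do the documents show that lung disease is the likeliest source of primary events; stroke and laboratory abnormalities are components too. Localization to the lung is not presented as a hazard: Section 1.2 links it to repair, and Sections 1.4 and A.2 describe infusions in COPD as safe. Finally, the per-event shifts of 20 and 10 points hold for an event of any cause. They describe the small groups rather than this criterion.

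**Conclusion.** The point holds in a limited form. Item 9 and its five counterparts carry a qualifier that does not fit a frailty trial and is not explained. As a result, one narrow class of terminal illness is left to discretion while an equal prognosis from any other organ is a firm exclusion.

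The size is 20 percentage points per background event in a pilot group and 10 in a randomized arm. The number of such subjects is not given, so no expected distortion can be calculated; a figure such as 20 points in one randomized arm would need two such subjects in the same arm, both with events within a month, and nothing in the documents supports assuming that. The link to 1-year survival is secondary, because that aim is exploratory and the primary endpoint is at one month.

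The conclusion rests on a literal reading of item 9 and of the composite. It does not depend on the wording having been carried over, which remains an inference. It is an eligibility inconsistency worth correcting, not a threat to the validity of the trial.

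**What to change.** Reconcile the criterion with the frailty indication and with item 5, in one of two ways. Either remove the qualifier *non-pulmonary* from synopsis item 10 and from item 9 in Sections 4.2, A.4.2, B.3.2, C.4.2 and D.4.2, so that the limit applies whatever the organ. Or keep it and state why pulmonary conditions are exempt and how item 9 is meant to work alongside item 5. The choice is for the sponsor; the six lists should agree.

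The first option costs one word in each of six lists, with the amendment approval that Section 10.2 requires. Its downside is that a few candidates with terminal lung disease become uniformly ineligible instead of being decided case by case. No endpoint, visit or analysis changes.
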